3.2. SCHEDULE OF EVENTS

Schedule of events can be found in Section 1.3 of the protocol.

3.3. CHANGES TO ANALYSES FROM PROTOCOL

There are no changes to the analyses planned in the protocol.

[figure not shown]
4. PLANNED ANALYSES

4.1. DATA AND SAFETY MONITORING BOARD (DSMB)

An independent DSMB will provide oversight, to ensure safe and ethical conduct of the study.

The DSMB will meet monthly and make any necessary recommendations to the Sponsor based on their evaluations of emerging data. In particular, the evaluation of 7-day safety data from participants dosed in Stage 1 will be performed by the DSMB, who will advise the sponsor on whether it is appropriate to proceed into Stage 2 of the study. The DSMB will also review study progress and monitor for evidence of harm resulting from AZD7442. If required, the DSMB will recommend temporarily stopping or termination of the study. There is no formal efficacy look by the DSMB with the potential for early stopping due to efficacy planned for this study.

Figure B: Study Dose Exposure Expansion

Further details, composition, and operation of the independent DSMB will be described in a DSMB Charter.

4.2. MORBIDITY ADJUDICATION COMMITTEE

An independent Morbidity Adjudication Committee (MAC) will be constituted to provide an independent, external, systematic, and unbiased assessment of blinded data to evaluate whether the causes of death for participants are considered COVID-19 associated. Only adjudicated deaths will be included in efficacy endpoints. All fatal events will be further assessed as part of safety evaluation. Further details of this adjudication will be provided in a separate Morbidity Adjudication Committee Charter.

4.3. INTERIM ANALYSIS

No interim analysis is planned.

4.4. PRIMARY ANALYSIS

The primary analysis will occur after approximately 24 primary endpoint events have been confirmed across the active and control groups or 30% of study participants have become unblinded (at which point the ability to observe primary endpoint events is expected to have diminished), whichever occurs earlier. All primary endpoint events accrued up until the data cut-off (DCO) will be included in the primary analysis. The date for the DCO for this analysis will be the date that the 24th primary endpoint event is confirmed or the date that 30% of study participants have become unblinded, whichever occurs earlier.

All planned primary analyses are detailed in this SAP and will be performed by AstraZeneca or its delegates following Sponsor authorization of this SAP, Sponsor authorization of the analysis sets, database lock (DBL), and

analysis team unblinding. The primary analysis will be carried out by an unblinded analysis team, and the procedure will be detailed in an unblinding plan; participant level unblinding information will be kept strictly confidential, and rationale for any unblinding will be documented.

4.5. FINAL ANALYSIS

The final analysis will be conducted at the end of the study, i.e., after the last participant dosed has completed the Day 457 visit.

All final, planned analyses are detailed in this SAP and will be performed by AstraZeneca or its delegates following Sponsor authorization of this SAP, Sponsor authorization of the analysis sets, DBL, and general study unblinding.

5. ANALYSIS SETS

5.1. ALL PARTICIPANTS ANALYSIS SET

The all participants analysis set (PAS) will contain all participants screened for the study. All participants analysis set is to be used for reporting disposition and screening failures.

All participants screened are those who provide informed consent.

5.2. FULL ANALYSIS SET

The Full Analysis Set (FAS) will contain all participants in the PAS who were randomized and received at least one of the planned injections of IMP, irrespective of their protocol adherence and continued participation in the study. Per the protocol a dose is two injections, but any participant receiving at least one injection will be included in the FAS based on intent-to-treat (ITT) principle. Participants will be analyzed according to their randomized treatment irrespective of whether they have prematurely discontinued, according to the ITT principle. Participants who withdraw consent to participate in the study will be included up to the date of their study termination.

For analyses and displays based on the FAS, participants will be classified according to randomized treatment regardless of what treatment they actually received.

5.3. FULL PRE-EXPOSURE ANALYSIS SET

The Full Pre-Exposure Analysis Set (FPAS) will contain all participants in the FAS who did not have a prior SARS-CoV-2 RT-PCR-positive confirmed COVID-19 infection.

For analyses and displays based on the FPAS, participants will be classified according to randomized treatment regardless of what treatment they actually received.

5.4. SAFETY ANALYSIS SET

The safety analysis set (SAF) will contain all participants in the PAS who received at least one of the planned injections of IMP. Per the protocol a dose is two injections, but any participant receiving at least one injection will be included in the SAF to account for safety in all participants receiving any injection.

For analyses and displays based on SAF, participants will be classified according to the actual treatment received. Erroneously-treated participants (e.g., those randomized to treatment A, but were actually given treatment B) are accounted for in this analysis set by assigning them to the treatment they actually received. A participant who has once or on several occasions received active IMP is classified as active.

5.5. PHARMACOKINETIC ANALYSIS SET

The PK analysis set will contain all participants in the PAS who received at least one injection of AZD7442 components and from whom PK blood samples are assumed not to be affected by factors such as protocol violations and who had at least one quantifiable serum PK observation post dose. Per the protocol a dose is two injections, but any participant receiving one injection will be accounted for in the corresponding individual mAb component.

For analyses and displays based on PK analysis set, participants will be included according to the actual treatment received. Participants who received placebo will not be included. Participants should be excluded from the PK analysis set if they were randomized to AZD7442 and instead received placebo, were randomized to placebo and instead received AZD7442, or received two injections of the same mAb component. Summaries will be displayed by the individual mAb components, AZD8895 and AZD1061. Participants who received only one mAb component should be excluded from both the AZD7442 total summary and the summary of the mAb component they did not receive.

5.6. ADA EVALUABLE ANALYSIS SET

The ADA evaluable analysis set will contain all participants in the SAF who have a non-missing baseline AZD7442 ADA result and at least one non-missing post-baseline AZD7442 ADA result. This analysis set is not defined in the protocol but is required for the analyses.

5.7. NAB EVALUABLE ANALYSIS SET

The SARS-CoV-2 nAb evaluable analysis set will contain all participants in the SAF from whom blood samples are assumed not to be affected by factors such as protocol violations, and who had at least one quantifiable serum titer observation post dose. Participants should be excluded from the SARS-CoV-2 nAb evaluable analysis set if they were randomized to AZD7442 and instead received placebo, were randomized to placebo and instead received AZD7442, received two injections of the same mAb component, or received only one mAb component. This analysis set is not defined in the protocol but is required for the analyses.

6. GENERAL CONSIDERATIONS

6.1. REFERENCE START DATE AND STUDY DAY

Study Day will be calculated from the reference start date and will be used to show start/stop day of assessments and events. Reference start date is defined as the day of the dose of IMP i.e., Day 1.

Study Day will be computed as follows:

- Study Day = (Date of event Date of dose of IMP) + 1 if the date of the event is on or after the date of the dose of IMP;
- Study Day = (Date of event Date of dose of IMP) if the date of the event is prior to the date of dose of IMP.

In the situation where the event date is partial or missing, Study Day and any corresponding durations will be displayed as missing in the listings.

For illness visits, an illness study day will be calculated. The reference start date is defined as the day of first illness assessment, i.e., illness visit Day 1. This will be calculated separately for each illness episode.

Illness Study Day will be computed as follows:

• Illness Study Day = (Date of event – Date of illness visit Day 1) + 1.

Partial dates

Partial dates for unblinding and COVID-19 vaccination/COVID-19 preventative product in which the month and/or year are missing are not expected. However, imputation rules are specified as follows: in cases where the day is missing, then day will be imputed as the first of the month. In cases where the month is missing, then month will be imputed as the later of January or month of IMP administration. If the date is completely missing, the date will be imputed as the day after IMP administration.

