16.1.3. PRIMARY ESTIMAND

The treatment condition of interest is single dose of AZD7442 (two IM injections, one for each mAb component, AZD8895 and AZD1061). The alternative treatment condition to which comparison will be made is a placebo.

The population of participants targeted in the primary estimand includes adults at least 18 years of age who have not had a prior SARS-CoV-2 RT-PCR-positive confirmed COVID-19 infection and who are candidates for benefit from passive immunization with antibodies, defined as having increased risk for inadequate response to active immunization (predicted poor responders to vaccines OR intolerant of vaccine), OR having increased risk for SARS-CoV-2 infection, defined as those whose locations or circumstances put them at appreciable risk of exposure to SARS-CoV-2 and COVID-19.

The primary endpoint (variable) to be obtained is a binary response, whereby a participant is defined as a COVID-19 case if their first case of SARS-CoV-2 RT-PCR-positive symptomatic illness occurs post dose of IMP prior to Day 183.

The primary estimand uses a while on treatment strategy. Data for participants who become unblinded to treatment assignment and/or take COVID-19 vaccine or other COVID-19 preventive product, in both cases prior to having met the criteria for the primary efficacy endpoint, are censored at the date of unblinding/receipt of first dose of COVID-19 preventive product, whichever is earlier.

The population-level summary measure is prophylactic efficacy, calculated as 1 – relative risk (RR). (RR is the incidence of infection in the AZD7442 group relative to the incidence of infection in the control group.)

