16.1.4. PRIMARY ANALYSIS OF PRIMARY EFFICACY ENDPOINT

The primary efficacy analysis of the primary endpoint will be performed on the FPAS. Participants who withdraw from the study prior to having met the criteria for the primary efficacy endpoint will be censored (considered as not having the event) at the time of last observation. Participants with deaths that are caused by SARS-CoV-2 (death related to COVID marked on the death eCRF page) will be considered as having the event, even if no other qualifying symptoms are met. Participants with hospitalizations due to COVID-19 will also be considered as having the event.

A Poisson regression model with robust variance (Zou, 2004) adjusting for follow-up time, will be used as the primary efficacy analysis model to estimate the RR on the incidence of SARS-CoV-2 RT-PCR-positive symptomatic illness occurring post dose of IMP between the AZD7442 and the placebo groups. The model contains the planned treatment group and age group at the time of informed consent (i.e., ≥ 60 years and < 60 years, see Section 7.6) as a covariate. The logarithm of the participant's corresponding follow-up time at risk starting from dose up to the study day 183 visit will be used as an offset variable in the model to adjust for participants having different exposure times during which the events occur. Participants who withdraw or have a non-COVID-19 related death prior to meeting the primary endpoint will not be counted as having the event. The follow up time for those participants will be at that time relative to dose. Calculation of follow-up time is detailed as following:

- For participants who meet the primary endpoint before Day 183, the follow-up time will be calculated as (Date of Onset of Primary Endpoint) (Date of Dosing) + 1. Date of Onset of Primary Endpoint is defined as the assessment date of qualifying COVID symptoms, if associated with a positive SARS-CoV-2 RT-PCR lab test from a sample collected within the 5 days prior to symptom assessment through 10 days after symptom assessment. In the case of death due to COVID-19 or hospitalization due to COVID-19, the Date of Onset of Primary Endpoint is the earliest date of death/date of hospital admission when a qualifying symptom assessment is not observed.
- For participants who do not experience a primary endpoint before Day 183, the efficacy follow-up time will be considered censored and determined based on the following:

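### SAP 6.1 sets a missing day in an unblinding or COVID-19 product date to the 1st of the month with no floor at dosing, so the censoring date can precede dosing and the log offset be undefined

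*SAP*

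**What the plan says.** SAP 6.1, under partial dates, has three rules for unblinding and for COVID-19 vaccine or preventive-product dates:

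- Day missing: "in cases where the day is missing, then day will be imputed as the first of the month".
- Month missing: the "month will be imputed as the later of January or month of IMP administration". No year is attached to either month.
- Everything missing: "If the date is completely missing, the date will be imputed as the day after IMP administration".

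The same paragraph says that partial dates "in which the month and/or year are missing are not expected". It says nothing on how often only the day will be missing.

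Under the primary estimand (SAP 16.1.3), data for participants with either intercurrent event before meeting the endpoint "are censored at the date of unblinding/receipt of first dose of COVID-19 preventive product, whichever is earlier". In SAP 16.1.4 the logarithm of "follow-up time at risk starting from dose up to the study day 183 visit will be used as an offset variable". Neither section says what to do if follow-up comes out at zero or below.

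**The concern.** Only the completely-missing rule is tied to the full dose date. The other two can return a date before the participant was dosed. The result is also out of order: knowing nothing about the date gives a usable value, while knowing the month and year can give an impossible one.

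These dates close the at-risk period. A pre-dose value makes follow-up zero or negative, its logarithm does not exist, and a participant who belongs in the full pre-exposure analysis set would drop out of the primary model. The SAP does not announce this exclusion.

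The same censoring dates serve the key secondary, other secondary and Day 366 estimands (SAP 2.4), the per-protocol estimand (Table N) and the all-cause mortality estimand (Table P). The hypothetical estimand uses the date of the first intercurrent event as the onset of an imputed event (SAP 16.1.8.1, Step 2), so it inherits the error too.

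**Working it through.** The plan gives no count or figure for partial dates, so there is nothing of its own to reproduce. The check is calendar arithmetic. The calendar years are assumed for illustration.

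**Formula.** SAP 16.1.4 computes follow-up as (end date - date of dosing) + 1 for events and for end of study. It gives no separate formula for an intercurrent event, so I assume the same form.

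1. *Day missing, dosing month.* Dose 15 January 2021, product recorded as January 2021. Imputed date 1 January 2021; follow-up = (1 - 15) + 1 = -13 days, and log(-13) is undefined. A dose on the 2nd gives (1 - 2) + 1 = 0, and log(0) is undefined too. A dose on 31 January gives (1 - 31) + 1 = -29, the extreme. A dose on the 1st gives 1 day, which is usable.

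2. *Only the dosing year known.* Dose 15 January 2021, product recorded as 2021. The later of January and the dosing month is the dosing month, and the day becomes the 1st. The date is the same as in step 1, and so is the failure.

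3. *How often, given a dosing-month date.* Every dose day fails except the 1st: 365 - 12 = 353 of 365 dose dates (96.7%).

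4. *How often, among all day-missing dates.* Assume dose dates uniform over a 365-day year and true intercurrent dates uniform over Days 1 to 182. In a month of L days, doses on days 2 to L leave (L - 1) + (L - 2) + ... + 1 = L(L - 1)/2 failing pairs of dose day and true date. Over the year: 7 × 465 + 4 × 435 + 378 = 5,373. All pairs: 365 × 182 = 66,430. Share = 5,373 / 66,430 = 8.1%.

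5. *What a failing record is worth.* A dose on the 2nd with a true date on the 31st has true follow-up of (31 - 2) + 1 = 30 days, which is the most any failing record can have. With a floor at the day after dosing it contributes 2 days; without one it contributes nothing.

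6. *Scale of one event.* Protocol 2.3.2 reports 25 cases and 77% efficacy (95% CI 46 to 90) but no split by arm. Assuming 8 v 17 with 2:1 allocation and equal follow-up, efficacy = 1 - (8/2)/17 = 76.5%. With 7 v 17 it is 1 - 3.5/17 = 79.4%; with 8 v 16 it is 1 - 4/16 = 75.0%. One event therefore moves the estimate by 1.5 to 2.9 points, which is small beside that interval.

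7. *With the floor.* In step 1 the later of 1 January and 16 January is 16 January; follow-up = (16 - 15) + 1 = 2 days, and the offset is defined.

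**The case against.** The best defence is that anchoring to dosing was plainly intended. The month rule refers to the dosing month, the completely-missing rule uses the day after dosing, time at risk starts at dosing, and SAP 16.1.4 gives 1 day to participants with no post-baseline data. The loss of the record is also software behaviour, not SAP text. Both points are fair, but the intent is not written into the missing-day rule, and no other section supplies the floor.

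The defence also says that little is at stake, because failing records have short true follow-up. The treatment policy estimand, formally tested second (SAP 7.4 and 16.1.9), does not censor at these dates. That stands, and it limits the size of the point.

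Three stronger readings may tempt a reader, and the documents do not support them:

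- *The month rule can put censoring nearly a year late.* For a dose on 15 December 2020 with only 2021 recorded, comparing month names gives 1 December 2021 (Day 352), past Day 183. On that reading January could never be the later month and the word would be redundant. Read chronologically, the date is 1 January 2021 (Day 18). The SAP also does not expect missing months. The wording should name the years, but a late date is not a demonstrated error.
- *The rule fails for about 97% of dates.* That share applies only when the intercurrent event falls in the dosing month. The figure for day-missing dates in general is about 8% under the uniform assumption.
- *The rule wrongly discards true events.* Suppose dosing on 5 January 2021, an event on 10 February and a product date recorded as February. The event then falls after the imputed 1 February. But with the day unknown, the order of the event and the product is unknown as well. Censoring at the earliest consistent date is a defensible convention.

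**Conclusion.** The missing-day rule, and the month rule when only the dosing year is known, can return a censoring date before dosing. For a date in the dosing month this happens for every dose day except the 1st. The primary model's offset is then undefined, and nothing in the SAP repairs it. This follows from the text under any reading, given the follow-up formula assumed above.

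The practical size is probably small. The number of partial dates is not given. The 8.1% share rests on uniform dates, and the effect of a single event rests on an assumed 8 v 17 split. A non-case restored by the floor adds 2 days. The floor would not bring back an event between the imputed and the true date, except one on Day 1 or 2. This is a wording defect worth a cheap correction, not a threat to the primary conclusion.

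**What to change.** In SAP 6.1, add that the imputed unblinding or product date is the later of the date given by the missing-day or missing-month rule and the day after IMP administration. For the missing month, state that January means January of the reported year and the dosing month means that month in the dosing year, so that the comparison is chronological.

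Optionally, repeat the primary analysis with the latest date consistent with the known parts. Do not use a different censoring rule for participants with an observed event in the imputed month: keeping their events while stopping non-cases at the 1st would make censoring depend on outcome.

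The cost is a few lines of text and one derivation change. Protocol 2.3.2 already reports a primary analysis, so the change should be documented as made afterwards. Count first the records with follow-up of zero or below. If there are none, no rerun is needed for this reason; if there are some, rerun and report both results.

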6.2. BASELINE

Unless otherwise specified, baseline is defined as the last non-missing measurement taken prior to the dose of IMP. In the case where the last non-missing measurement and the date and time of the dose of IMP coincide or where time is missing, that measurement will be considered baseline, but adverse events (AEs) and medications commencing on the date and time of the dose of IMP will be considered post-baseline.

Illness Visit baseline is defined as the first non-missing measurement taken on Illness Visit Day 1. If there is no non-missing measurement available on Illness Visit Day 1, Illness Visit baseline is considered as missing. For instances where Illness Visit Day 1 occurs on the same day as a main study Visit, and Illness Visit Day 1 measurements are missing, then the measurements from the main study Visit will be used as Illness Visit baseline. Otherwise if there is still no available measurement for Illness Visit Day 1, Illness Visit baseline is considered as missing.

6.3. UNSCHEDULED VISITS, RETESTS, AND EARLY TERMINATION DATA

For by-visit summaries, data recorded at the nominal visit will be presented. That is, unscheduled, retest (same visit number assigned), and early termination measurements will not be included in by-visit summaries but might contribute to the baseline timepoint and/or maximum value, where required (e.g. shift table). Visits for human biological samples data will follow a windowing convention as described in Section 6.4.

Listings will include scheduled, unscheduled, retest and early discontinuation data.

6.4. WINDOWING CONVENTIONS

A windowing convention will be used to determine the analysis value for a given study visit for human biological samples data analyses. The window definitions as following will be used for the following assessments:

- Main study: serum sample for SARS-CoV-2 serology (anti-nucleocapsid testing)
- Main study: serum sample for AZD7442 pharmacokinetic assessment (PK)
- Main study: serum sample for AZD7442 ADA assessment (ADA)
- Main study: serum sample for SARS-CoV-2 nAbs assessment (pharmacodynamic [PD])
- Main study: serum sample exploratory biomarkers
- Main study: participant subset only: nasal adsorption for exploratory assessments (PK)
- Illness visits schedule: saliva sample for viral shedding
- Illness visits schedule: serum sample for AZD7442 pharmacokinetic assessment (PK)
- Illness visits schedule: serum sample for SARS-CoV-2 nAbs assessment (PD)
- Illness visits schedule: nasal adsorption for SARS-CoV-2 mucosal responses and exploratory assessments (PK)
- Illness visits schedule: serum sample for exploratory assessments

The window for the visits following baseline will be constructed in such a way that the upper limit of the interval falls halfway between the two visits (the lower limit of the first post-baseline visit will be Day 2). If an even number of days exists between two consecutive visits, then the upper limit will be taken as the midpoint value minus 1 day.

Table E: Analysis windows for serum sample for SARS-CoV-2 serology testing and serum sample exploratory biomarkers by Visit

Visit	Day Relative to Dose	Visit Window (Study Day)
Day 1	≤1	≤ 1

Day 8	8	2 - 18
Day 29	29	19 - 43
Day 58	58	44 - 74
Day 92	92	75 - 137
Day 183	183	138 - 274
Day 366	366	≥ 275

Table F: Analysis windows for serum sample for AZD7442 PK assessment and serum sample for SARS-CoV-2 nAbs assessment (PD)

Visit	Day Relative to Dose	Visit Window (Study Day)
Day 1	≤1	≤ 1
Day 8	8	2 - 18
Day 29	29	19 - 43
Day 58	58	44 - 74
Day 92	92	75 - 137
Day 183	183	138 - 274
Day 366	366	275 - 411
Day 457	457	≥ 412

Table G: Analysis windows for serum sample for AZD7442 ADA assessment by Visit

Visit	Day Relative to Dose	Visit Window (Study Day)
Day 1	≤ 1	≤ 1
Day 29	29	2 - 43
Day 58	58	44 - 120
Day 183	183	120 - 274
Day 366	366	275 - 411
Day 457	457	≥ 412

Table H: Analysis windows for nasal adsorption for exploratory assessments by Visit

Visit	Day Relative to Dose	Visit Window (Study Day)	
Day 1	≤1	≤ 1	
Day 8	8	2 - 49	
Day 92	92	50 - 137	
Day 183	183	138 - 274	
Day 366	366	≥ 275	

Table I: Analysis windows for serum sample for AZD7442 PK, serum sample for SARS-CoV-2 nAbs assessment (PD), and serum sample for exploratory assessments by Visit (Illness Visit Schedule)

Visit	Day Relative to Illness	Visit Window (Illness Day)	
Illness Day 1	≤1	≤ 1	

Illness Day 14	14	8 - 17
Illness Day 21	21	18 - 24
Illness Day 28	28	25 - 35

Table J: Analysis windows for Viral Shedding by Visit (Illness Visit Schedule)

Visit	Day Relative to Illness	Visit Window (Illness Day)
Illness Day 1	≤ 1	≤ 1
Illness Day 3	3	2 - 3
Illness Day 5	5	4 - 6
Illness Day 8	8	7 - 9
Illness Day 11	11	10 - 12
Illness Day 14	14	13 - 17
Illness Day 21	21	18 - 24
Illness Day 28	28	25 - 35

Table K: Analysis windows for nasal adsorption for exploratory assessments by Visit (Illness Visit Schedule)

Visit	Day Relative to Illness	Visit Window (Illness Day)
Illness Day 1	≤ 1	≤ 1
Illness Day 14	14	8 - 20
Illness Day 28	28	21 - 35

For assessments occurring during the Illness Visit Schedule, windows are applied only to illness episodes with laboratory confirmed positive RT-PCR test results. One or more results for a particular human biological samples variable may be obtained in the same visit window. In such an event, the result with the date closest to the expected visit date will be used in the analysis. In the event that two observations are equidistant from the expected visit date, the later observation will be used in the analysis.

